10.3 Clinical Laboratory Evaluation

Hematology analytes include hemoglobin, hematocrit, red blood cell (RBC), platelet, white blood cell (WBC) and differentials (neutrophils, lymphocytes, monocytes, basophils, and eosinophils), mean corpuscular volume (MCV), mean corpuscular hemoglobin (MCH), and mean corpuscular hemoglobin concentration (MCHC).

Serum chemistry analytes include aspartate aminotransferase (AST), alanine aminotransferase (ALT), alkaline phosphatase (ALP), gamma-glutamyl transferase (GGT), albumin, creatinine, calculated creatinine clearance, calcium, glucose, total protein, total bilirubin, sodium, potassium, chloride, bicarbonate, blood urea nitrogen, lactate dehydrogenase, and uric acid.

Coagulation analytes include partial thromboplastin time and prothrombin time.

Descriptive statistics will be provided for baseline, each post-baseline and change from baseline at each post-baseline assessment. A shift table comparing the CTCAE grade at baseline to each post-baseline assessment will be provided for analyte with CTCAE grades. In addition, a shift table comparing the CTCAE grade at baseline to the worst post-baseline assessment will be provided.

Additional laboratory values including creatinine kinase, thyroid stimulating hormone, free thyroxine (T4), lipase, amylase, and HLA typing will be summarized by descriptive statistics at baseline and each post-baseline assessment.

Urinalysis analytes include specific gravity, pH, glucose, protein, bilirubin, ketones, leukocytes, esterase, and blood. For subjects with positive protein and white blood cell or blood during urinalysis, microscopic examination will be performed and include RBCs, WBCs, epithelial cells, bacteria, crystals, and casts.

All laboratory data will be listed by subject.

10.4 Vital Signs

Vital signs include weight, heart rate (HR), respiratory rate, temperature, supine systolic blood pressure (SBP), supine diastolic blood pressure (DBP) and oxygen saturation. Descriptive statistics will be provided for each vital sign at baseline, post-baseline, and for change from baseline at each post-baseline assessment.

All vital sign data will be listed by subject.

10.5 Electrocardiogram

Electrocardiogram (ECG) assessments include PR, RR, QRS, QT, correct QT interval using Fredericia's formula (QTcF), corrected QT interval using Bazett's formula (QTcB), and HR. Each analyte will be collected in triplicate at every baseline and post-baseline ECG assessment. Descriptive statistics will be provided for the mean of the triplicate at baseline, post-baseline and change from baseline at each post-baseline assessment.

The number and percentage of subjects in each of the following categories based on QTcB and QTcF will be provided:

- QTc interval ≥ 450 ms,
- QTc interval ≥ 480 ms,
- QTc interval ≥ 500 ms,
- QTc interval change from baseline ≥ 30 ms,
- QTc interval change from baseline ≥ 60 ms.

In addition, the interpretation of ECGs will be categorized as normal or abnormal at each assessment time point. Shift tables will be provided to summarize ECG interpretation change from baseline at each post-baseline assessment.

Echocardiogram includes stress test (normal and abnormal) and left ventricular ejection fraction (LVEF). Descriptive statistics will be provided for LVEF at baseline, post-baseline and for change from baseline at each post-baseline assessment. The number and percentage of subjects who performed a stress test at baseline and at each post-baseline assessment time point will be provided.

11 IMMUNOGENICITY

Validated assays will be used to determine the anti-drug antibodies to NKTR-214. The number and percentage of subjects who have detectable anti-NKTR-214 antibodies will be summarized for subjects in the safety population who provide at least 1 post-treatment sample.

All immunogenicity data will be listed by subject.

12 EXPLORATORY ANALYSES

TBD

13 PHARMACOKINETICS

Pharmacokinetic data collected on the case report forms will be presented in data listings. Details for pharmacokinetic analyses will be provided in a separate analysis plan.

14 CHANGES TO PROTOCOL-SPECIFIED ANALYSES

No changes from the protocol specified analyses are planned.

16 APPENDICES

16.1 Evaluation of Overall Response using RECIST 1.1

Overall response first time point	Overall response subsequent time point	Best overall response
CR	CR	CR
CR	PR	SD, PD, or PR ^a
CR	SD	SD provided minimum criteria for SD duration met, otherwise, PD.
CR	PD	SD provided minimum criteria for SD duration met, otherwise, PD.
CR	NE	SD provided minimum criteria for SD duration met, otherwise, NE.
PR	CR	PR
PR	PR	PR
PR	SD	SD
PR	PD	SD provided minimum criteria for SD duration met, otherwise, PD.
PR	NE	SD provided minimum criteria for SD duration met, otherwise, NE.
NE	NE	NE

Abbreviations CR, complete response; PR, partial response; SD, stable disease, PD; progressive disease; NE, inevaluable.

^a If a CR is truly met at first time point, then any disease seen at a subsequent time point, even disease meeting PR criteria relative to baseline, makes the disease PD at that point (since disease must have reappeared after CR). Best response would depend on whether minimum duration for SD was met. However, sometimes 'CR' may be claimed when subsequent scans suggest small lesions were likely still present and in fact the subject had PR, not CR at the first time point. Under these circumstances, the original CR should be changed to PR and the best response is PR. Source: Eisenhauer, 2009

16.2 Preferred Terms for searching AEs of Special Interest in Safety Analysis

AEs of Special Interest	PTs (MedDRA V20.1)
Rash	erythema
	rash erythematous
	rash maculo-papular
	rash papular
	rash pruritic
	rash pustular
	rash vesicular
	rash generalised
	rash macular
Flu like symptoms	influenza like illness
	pyrexia
	chills
	influenza
Hypotention	hypotension
	blood pressure decreased
Infusion related reaction	infusion related reaction
	hypersensitivity
Pruritus	pruritus
	pruritus generalised
	eye pruritus
	pruritus allergic
Fatigue	asthenia
	fatigue
	decreased activity
	lethargy
	malaise
Angioedema	angioedema
	face oedema
	eye oedema
	eye swelling
	lip oedema
	lip swelling
	mouth swelling
	oedema mouth
	periorbital oedema
	swelling face
	swollen tongue
	tongue oedema
	urticaria

Table continues

AEs of Special Interest	PTs (MedDRA V20.1)
Syncope	syncope
	presyncope
Hepatic Function Abnormal	alanine aminotransferase increased
	aspartate aminotransferase increased
	hepatic enzyme increased
	hepatitis
	hepatitis acute
	liver disorder
	liver function test abnormal
	transaminases increased
	autoimmune hepatitis
Hypothyroidism/Thyroiditis	autoimmune hypothyroidism
	hypothyroidism
	thyroid stimulating hormone deficiency
	autoimmune thyroiditis
	blood thyroid stimulating hormone decreased
	blood thyroid stimulating hormone abnormal
	blood thyroid stimulating hormone increased
	thyroiditis
Hyperthyroidism	hyperthyroidism
Pneumonitis	acute respiratory distress syndrome
	acute respiratory failure
	interstitial lung disease
	lung infiltration
	pneumonitis
	acute interstitial pneumonitis
	acute lung injury
Pancreatitis/Pancreatic enzyme elevation	pancreatitis
	pancreatitis acute
	amylase abnormal
	amylase increased
	lipase abnormal
	lipase increased
	pancreatic enzymes abnormal
	pancreatic enzymes increased
Vitiligo	skin hypopigmentation
	vitiligo

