## 6.10 Dose Modifications

### 6.10.1 Non-immune-related Adverse Events

- Grade 1 or 2 toxicity: No requirement for dose delay or dose reduction. If the toxicity persists at Grade 2 following completion of Cycle 1, a dose reduction to the next lower NKTR-214 dose level (for dose escalation) or 50% of the assigned dose (dose escalation or dose expansion) may be implemented at the discretion of the Investigator with the approval of the Medical Monitor.
- Grade 3 toxicity: NKTR-214 may be withheld if toxicity cannot be managed by adequate medical intervention. NKTR-214 dosing may resume at the same dose or the next lower NKTR-214 dose level (for dose escalation) or 50% of the assigned dose (dose escalation or dose expansion) when toxicity resolves to Grade 1 or returns to baseline, except for instances consistent with clinically significant capillary leak syndrome or where the potential recurrence of the event poses an undue risk for the subject.
- Grade 4 toxicity (excluding Grade 4 transient lymphopenia < 14 days in duration): Dosing should be permanently discontinued.

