### 6.10.2 Immune-related Adverse Events

Permanently discontinue NKTR-214 for:

- Grade 2 or 3 immune-related AEs (irAEs) that do not improve to Grade 0 or 1, except endocrinopathies managed with replacement hormones
- Grade 3 irAEs that recur at  $\geq$  Grade 3
- Grade 3 immune-related pneumonitis, colitis, hepatitis, pancreatitis

- Grade 4 irAEs, except endocrinopathies managed with replacement hormones
- Any uveitis event

Subjects who need more than 6 weeks to recover from treatment-related toxicities should be removed from study treatment.

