### 8.9 Immune-Related Adverse Event Reporting

Immune-related adverse events (irAE) are considered adverse events of special interest due to their potential clinical significance. Investigators should use clinical judgment to determine that an adverse event is immune related, and are encouraged to rule out neoplastic, infectious, metabolic, toxic or other etiologies, to the extent possible, before characterizing an event as immune related.

Grade 3 or higher immune-related adverse events, with an onset within **30 days** after the subject’s last dose of study treatment, must be reported to Nektar Therapeutics Drug Safety or its designee within **24 hours** of when the site becomes aware of the event.

[REDACTED]

[REDACTED]

- [REDACTED]
- [REDACTED]

The Investigator must complete the SAE Form, mark the report as an immune related adverse event and send the completed form via email or fax to Nektar Therapeutics Drug Safety. Any medication or other therapeutic measures used to treat the event will be recorded. A follow-up report will be emailed or faxed to Nektar Therapeutics Drug Safety as soon as additional details become available.

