### 10.5.2 Safety

The primary endpoints of the study are to determine the MTD with NKTR-214. Adverse events and toxicity will be evaluated according to NCI CTCAE version 4.03. Safety assessments will be performed by medical review of AEs and laboratory results.

Incidence rate of DLT will be tabulated by dose cohort for the DLT population.

Treatment emergent AEs (TEAEs) within each system will be summarized by preferred term, system organ class, NCI-CTCAE grade of severity, and relationship to the study treatment. Serious AEs and AEs leading to study drug discontinuation will also be summarized.

A TEAE is defined as an AE that was not present prior to treatment with study treatment, but appeared following treatment or was present at treatment initiation, but worsened during treatment. An AE that was present at treatment initiation, but resolved and then reappeared while the subject was on treatment, is a TEAE (regardless of the intensity of the AE when the treatment was initiated).

Vital signs (including change in weight) and clinical laboratory test results will be summarized descriptively by dose (for the dose escalation phase) and by tumor type (for the dose expansion phase). Any significant physical examination findings will be listed. ECG and echocardiogram data will be evaluated by central review and abnormalities, if present, will be listed. A separate listing and summary of all immune-related AEs (irAEs) will be provided. A listing and summary of subjects who discontinued study drug due to an adverse event will be provided.

A data listing for deaths will be provided.

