- NKTR-214 related TEAEs by severity grade, SOC, and PT,
- Grade \geq 3 TEAEs by SOC and PT,
- NKTR-214 Related Grade \geq 3 TEAEs by SOC and PT,

- Serious adverse event (SAEs) by SOC and PT,
- NKTR-214 Related SAEs by SOC and PT,
- TEAEs leading to NKTR-214 delay, interruption, or reduction by SOC and PT,
- TEAEs leading to NKTR-214 discontinuation by SOC and PT,
- TEAEs leading to death by SOC and PT,

Selected AEs of special interest will be grouped by pooled PTs, which are provided in Appendix 16.2. The number and percentage of subjects for each AEs of special interest will be presented.

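### The SAP specifies no immune-related AE output although the protocol promises one, and its pooled Rash group, as read, lacks the plain term 'rash'

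*SAP*

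**What the plan says.** **Immune-related AEs.** Protocol 8.9 states: "Immune-related adverse events (irAE) are considered adverse events of special interest due to their potential clinical significance". It leaves the classification to the investigator's clinical judgment. On reporting, Protocol 10.5.2 says: "A separate listing and summary of all immune-related AEs (irAEs) will be provided". The synopsis makes the same promise under Statistical Methods.

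**SAP outputs.** SAP 10.2 sets out 14 bulleted AE summaries: all, related, Grade 3 or higher, serious, dose-modifying, discontinuation and fatal events, in various breakdowns. It also plans a summary of the duration of related events and a special-interest table: "Selected AEs of special interest will be grouped by pooled PTs, which are provided in Appendix 16.2". SAP 14 closes with "No changes from the protocol specified analyses are planned".

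**The term list.** Appendix 16.2, headed "Preferred Terms for searching AEs of Special Interest in Safety Analysis", has 14 groups and 76 preferred terms. The Rash group has nine: erythema, and rash qualified as erythematous, maculo-papular, papular, pruritic, pustular, vesicular, generalised and macular.

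**Events named for dosing action.** Protocol 6.10.2 names "Grade 3 immune-related pneumonitis, colitis, hepatitis, pancreatitis" and "Any uveitis event". Capillary leak is named in 6.10.1, the non-immune section, in the words "except for instances consistent with clinically significant capillary leak syndrome".

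**The concern.** Safety and tolerability is a primary objective, and the drug acts by stimulating the immune system. Which events investigators judged immune-related is therefore a central safety question. The protocol commits to answering it in a dedicated output. A programmer working from SAP 10.2 would not build that output, and a reader of SAP 14 would not know that anything was left out.

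The Rash group is a separate matter of definition. A pooled group exists to count distinct subjects with any of several related terms. If the plainest term is missing, the table reports a number smaller than its label implies.

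**Working it through.** **1. The irAE output**

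| Question | Protocol | SAP |
|---|---|---|
| Are irAEs of special interest? | Yes (8.9) | Special interest is defined by a fixed term list (10.2, Appendix 16.2) |
| How is an irAE identified? | Investigator judgment (8.9) | Not stated |
| Is there a separate summary and listing? | Yes (10.5.2, synopsis) | None among the 14 summaries in 10.2 |
| Is a departure declared? | n/a | No; SAP 14 says none is planned |

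In the visible SAP text, irAE appears only in the abbreviation list. The general tables cannot stand in for the missing output, because a row by preferred term does not show which events were judged immune-related. Nor can the Appendix 16.2 groups: they collect terms whatever the attribution, and they include items such as flu-like symptoms, fatigue and syncope.

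The data source also needs stating. For Grade 3 or higher irAEs, Protocol 8.9 has the investigator mark the report form as immune-related. The AE fields named in Protocol 8.2 do not include an immune-related designation, but that list is expressly not exhaustive and part of 8.9 is redacted. The visible text therefore does not show how lower grades are flagged.

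**2. The Rash group**

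Each term was checked for membership among the 76 in Appendix 16.2:

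- *rash*: absent
- *pneumonitis*, *hepatitis*, *pancreatitis*: present
- *colitis*, *uveitis*, *capillary leak syndrome*: absent, and no listed term contains these words

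Eleven of the 14 groups contain their own plain name: hypotension, infusion related reaction, pruritus, fatigue, angioedema, syncope, hypothyroidism/thyroiditis, hyperthyroidism, pneumonitis, pancreatitis and vitiligo. The other three are Rash, Flu like symptoms and Hepatic Function Abnormal.

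*Size.* The plan gives no figure to reproduce and no rash rate. Assume 20 of 50 subjects have any rash; 50 is the approximate size of each study part in SAP 4. Let s be the share of those 20 coded only to *rash*. The reported pooled count is then 20 × (1 − s).

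| s | Left out | Reported count | Reported rate | Rate with *rash* included |
|---|---|---|---|---|
| 10% | 20 × 0.10 = 2 | 18 | 18/50 = 36% | 20/50 = 40% |
| 25% | 20 × 0.25 = 5 | 15 | 15/50 = 30% | 40% |
| 50% | 20 × 0.50 = 10 | 10 | 10/50 = 20% | 40% |
| 75% | 20 × 0.75 = 15 | 5 | 5/50 = 10% | 40% |

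*Can the tables repair it?* Not exactly. SAP 10.2 counts a subject once within each summary level, so a subject with two rash terms appears in two rows. If the pooled group shows a subjects and the *rash* row shows b, the right count lies anywhere from max(a, b) to a + b. With a = 10 and b = 10, that is 10 to 20. The exact number has to come from subject-level data.

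**The case against.** **SAP 10.2 is silent; it does not withdraw the protocol's output.** SAP 14 could mean that the irAE summary stands as the protocol describes it, and SAP 5 lists all collected data. This is fair as to intent. But the SAP says its purpose is to give the details of the analyses, and it gives none here: no definition, no data source and no table. A general data listing is not the separate listing and summary promised.

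**The *rash* row may have been lost when the PDF was read.** This cannot be excluded, since the appendix is a table split across pages. That part of the point is therefore conditional on a check. The irAE part does not depend on the table.

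**The consequences are limited.** This stands. The analyses are descriptive, and the rules for dose escalation and for suspending expansion accrual use dose-limiting toxicities, not special-interest groups.

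A reader might go further and infer any of the following, none of which the documents support:

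- *That rash, colitis, uveitis or capillary leak would be missing from the safety report.* SAP 10.2 tabulates all treatment-emergent AEs by preferred term, grade, relatedness and seriousness, and separately those leading to discontinuation. It also lists every AE by subject.
- *That the special-interest table would show zero colitis or uveitis.* Where there is no group, no count is reported at all.
- *That the list must cover every event in Protocol 6.10.* SAP 10.2 calls the groups selected, and the protocol identifies irAEs by judgment, not by term search.
- *That capillary leak is an omitted immune event.* The protocol names it in 6.10.1, the non-immune section.

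**Conclusion.** The point holds in two places. The irAE listing and summary promised by the protocol is not specified in the SAP, and SAP 14 does not acknowledge this; that follows directly from the text. The pooled Rash group, as read, omits the plain term, so the count would be too low by the number of subjects coded only to it.

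The illustrated fall from 20 to between 18 and 5 subjects rests on three assumptions: the 20-of-50 rate, the 10% to 75% shares, and a plain *rash* term being available in the coding dictionary and used. None of these is given in the documents.

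The effect is confined to the pooled Rash count and the irAE output. It should be corrected because it concerns reporting on a primary objective, but it does not undermine the rest of the AE reporting.

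**What to change.** 1. **SAP 10.2:** add a summary of investigator-designated irAEs by system organ class, preferred term and grade, with a by-subject listing. State where the designation is recorded for every grade. Alternatively, declare the removal in SAP 14 and justify it.
2. **Appendix 16.2:** check the Rash group against the source PDF, and add *rash* if it is missing.
3. **Optional:** colitis and uveitis, named in Protocol 6.10.2, have no special-interest group; either add groups or record why they are left out. The same choice applies to capillary leak syndrome, as an event from the non-immune section.

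The cost is a few lines of SAP text, one table and one listing. If the irAE designation turns out not to be recorded below Grade 3, the SAP should say so, or the designation will have to be collected, which costs more.
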